4 STUDY DESIGN

4.1 OVERALL DESIGN

This is a multi-center, randomized, partially double-blind, and placebo-controlled **Phase Ib safety clinical trial** of inhaled CO (iCO) for the treatment of pneumonia and/or sepsis-induced ARDS. We hypothesize that low dose iCO will be safe and well-tolerated and that the CFK equation-based iCO personalized dosing algorithm will be accurate in achieving a target COHb level of 6-8% in patients with pneumonia and/or sepsis-induced ARDS.

Intubated subjects (n=36) with pneumonia and/or sepsis-induced ARDS who have consented to participate will be randomized in a 2:1 ratio to treatment with iCO (n=24) or medical grade air (n=12) for 90 minutes daily for 3 consecutive days. Subjects will be administered iCO or placebo air via inhalation through the mechanical ventilator using the CO Delivery System (COeventDS, 12th Man Technologies). Subjects randomized to CO will be administered iCO at an individualized dose between 200-500 ppm as determined by a personalized iCO dosing algorithm to achieve a COHb level of 6-8%. Subjects randomized to placebo will receive medical grade air through the COeventDS from identical appearing gas cylinders. The study drug will be administered for up to 3 days following randomization or until discontinuation of mechanical ventilation, whichever occurs first. For patients who have a tracheostomy, the equivalent of extubation for the purposes of this protocol will be breathing via tracheostomy with unassisted breathing.

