6.1.6 DAILY HOLD PARAMETERS PRIOR TO STUDY DRUG ADMINISTRATION

Subjects will be assessed daily prior to study drug administration as described in the **Schedule of Activities (Section 1.3)**.

Administration of the study drug will be held if the following criteria are met.

- COHb level $\geq 3\%$
- Lactate ≥ 4 mmol/L
- ST elevation MI or unstable angina/non ST elevation MI concerning for ACS
- Unstable atrial or ventricular arrhythmia

Subjects will have blood drawn daily for measurement of COHb and lactate prior to administration of study drug. If COHb $\geq 3\%$ or lactate ≥ 4 mmol/L, the study drug will be held until the next scheduled dose the following day. Lactate and COHb will be measured the following day to determine whether the study drug will be administered. If the study drug is being held for another reason, COHb levels will not be measured on days the study drug is being held.

A 12 lead EKG will also be performed and reviewed daily by the study staff physician prior to study drug administration to evaluate for cardiac exclusion criteria (eg. acute MI, acute coronary syndrome (ACS), or unstable atrial or ventricular arrhythmia). If a subject meets the following criteria for ST elevation MI or unstable angina/non ST elevation MI concerning for ACS according to the American College of Cardiology Foundation/American Heart Association guidelines¹⁴⁰⁻¹⁴², they will be excluded from enrollment or further study drug administration according to exclusion criteria.

ST elevation MI (STEMI) Criteria: New ST elevation at the J point in at least 2 contiguous leads of ≥ 2 mm (0.2 mV) in men or ≥ 1.5 mm (0.15 mV) in women in leads V2–V3 and/or of ≥ 1 mm (0.1 mV) in other contiguous chest leads or the limb leads; New or presumably new left bundle branch block (LBBB)¹⁴⁰⁻¹⁴².

Unstable angina/non ST elevation MI (NSTEMI): Ischemic ST-segment depression ≥ 0.5 mm (0.05 mV) or dynamic T-wave inversion with pain or discomfort; Nonpersistent or transient ST-segment elevation ≥ 0.5 mm for < 20 minutes. Threshold values for ST-segment depression consistent with ischemia are J-point depression 0.05 mV (-0.5 mm) in leads V2 and V3 and -0.1 mV (-1 mm) in all other leads (men and women)¹⁴⁰⁻¹⁴².

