9.2 SAMPLE SIZE DETERMINATION

As the primary endpoint of this Phase Ib trial is safety, this sample size of 36 (2:1 CO:placebo) was chosen based on a probability to estimate the mean difference between measured and predicted COHb levels in the CO group within 0.5% with 95% confidence to support the accuracy of the CFK equation.

Our preliminary data from our Phase Ia trial demonstrate that the CFK equation is highly accurate at predicting COHb levels following a 20 minute exposure to 200 ppm iCO ($r=0.916$, $R^2=0.9204$; $p<0.0001$). The mean difference between measured and predicted COHb levels was 0.1467 ± 0.2738 . Using a more conservative estimate of standard deviation (SD)=0.6, we will have >99% probability that 95% confidence intervals around the mean difference between measured and predicted COHb levels will be -0.353% to 0.647%. Our calculation includes an 8% dropout rate.

The goal of the safety evaluation for this study is to identify safety concerns associated with CO administration. The ability of the study to detect administration-related AEs or SAEs can be expressed by the true event rate above which at least one SAE would likely be observed and the true event rate below which no events would likely be observed. Specifically, for the CO arm of the study (n=24), there is a 90% probability of observing at least one AE if the true background rate of that AE is 10% and a 97% probability of observing at least one AE if the true background rate of that AE is 15%. For the placebo arm of the study (n=12), there is an 83% probability of observing at least one AE if the true background rate of that AE is 15% and a 91% probability of observing at least one AE if the true background rate of that AE is 20%. In our Phase Ia trial, there were no administration-related AEs and no SAEs related to study product or procedures.

Probabilities of observing one or more events between the groups are presented in **Table 6** below for a range of possible true AE rates. These calculations provide a more complete picture of the sensitivity of this study design to identify potential safety problems with CO.

Table 6. Probability of observing 1 or more events between the groups for different true AE rates

| CO group | | | Placebo Group | | |
|----------|--------------|-----------------------------|---------------|--------------|-----------------------------|
| n | True AE rate | Power to detect ≥ 1 AE | N | True AE rate | Power to detect ≥ 1 AE |

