9.4.2 ANALYSIS OF THE PRIMARY SAFETY ENDPOINT(S)

We hypothesize that iCO will be safe and well-tolerated and that our iCO dosing algorithm will be accurate

in achieving target COHb levels.

We will examine all AEs including pre-specified administration-related AEs by the type of event, as well as by body system class, and will report proportions and 95% CI. We will compare the occurrence of specific AEs in each arm by the χ^2 test, and the number of AEs per patient in each arm by the Wilcoxon-Mann-Whitney test.

COHb levels will be summarized descriptively reporting mean, standard deviation, median, minimum, and maximum at each time point, each day, by treatment arm. The mean difference between predicted and measured COHb levels with 95% confidence intervals will be presented for the iCO group. Repeated measures analysis of variance (ANOVA) will be used to assess the effects of treatment, time (over 3 days), and the interaction between time and treatment for 90-minute COHb levels. ANOVA will be repeated to assess the effects of treatment, time (over 3 days), entry criteria (ARDS/Sepsis vs. Non-ARDS/Sepsis Pneumonia vs. Non-ARDS/non-Sepsis Pneumonia), and two-way/three-way interactions of time, treatment and entry criteria. We will also compare the occurrence of COHb $\geq 10\%$ in each arm by the χ^2 test.

Accuracy of the CFK equation-based personalized iCO dosing algorithm to achieve target COHb levels will also be analyzed by Spearman correlation and Bland-Altman plots using measured vs. predicted COHb levels and modeled using linear or non-linear regression.

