9.4.3 ANALYSIS OF THE SECONDARY ENDPOINT(S)

We also hypothesize that iCO will reduce the severity of ARDS as measured by lung injury score (LIS), $\text{PaO}_2/\text{FiO}_2$, oxygenation index (OI), and dead space fraction (Vd/Vt). These endpoints will be analyzed using repeated measures analysis of covariance (ANCOVA) to assess the effects of treatment, time, and the interaction between time and treatment, while incorporating between-patient variation in baseline measurements and important covariates including smoking, age, sex, and severity of ARDS. Age and sex will be considered as important biological variables in all analyses.

Interaction contrasts will include polynomial trends across time, focusing on a linear trend suggesting improvement and a quadratic trend suggesting that improvement is leveling off. As part of our analysis, we will also include the interaction between treatment and entry criteria (ARDS/Sepsis vs. Non-ARDS/Sepsis Pneumonia vs. Non-ARDS/non-Sepsis Pneumonia) in the model. Because the study is not powered for the interaction between treatment and entry criteria, that test will be exploratory. We will also perform post-hoc analyses within each criteria group to generate hypotheses for future study.

With 24 subjects in the CO group and 12 subjects in the placebo arm, we will have 80% power ($\alpha=0.05$) to detect a 0.95 difference in LIS between treatment arms, assuming a conservative SD of 0.8 (**Table 7**). We will also have 80% power to detect a 78.6 mm Hg difference in $\text{PaO}_2/\text{FiO}_2$, a 12.0 difference in OI, and a 0.14 difference in Vd/Vt between treatment arms, assuming SDs of 66, 10.1, and 0.12 respectively.

Table 7. Minimal detectable difference at 80% power.

| Endpoint | SD | Detectable Difference ($\alpha= 0.05$) |
|-----------------------------|-----|--|
| LIS | 0.8 | 0.95 |
| $\text{PaO}_2/\text{FiO}_2$ | 66 | 78.6 |

| Endpoint | SD | Detectable Difference ($\alpha= 0.05$) |
|----------|------|---|
| OI | 10.1 | 12.0 |
| Vd/Vt | 0.12 | 0.14 |

Ventilator-free days (VFDs), hospital- and ICU-free days, and Sequential Organ Failure Assessment (SOFA) scores will each be analyzed separately using ANCOVA with treatment arm as the main effect. Given our modest sample size, we will only be powered to see large changes.

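### Repeated measures ANOVA/ANCOVA is named without an estimation method; a classical fit would drop every subject with a missing day, and the protocol's own rules make missing days very likely

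*Combined protocol and SAP*

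**What the plan says.** Section 9.4.2, on the primary endpoints: "Repeated measures analysis of variance (ANOVA) will be used to assess the effects of treatment, time (over 3 days", plus their interaction, for 90-minute COHb. The model is then repeated with three entry-criteria groups and all two-way and three-way interactions. Section 9.4.5 gives the same text. Section 9.4.3, on Lung Injury Score (LIS), PaO2/FiO2, oxygenation index (OI) and dead space (Vd/Vt), says: "These endpoints will be analyzed using repeated measures analysis of covariance (ANCOVA". No section names an estimation method, a within-subject covariance or a rule for a day without a value.

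The protocol foresees days without a value:

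- Dosing runs for up to three days "or until discontinuation of mechanical ventilation, whichever occurs first" (section 4.1).
- If pre-dose COHb or lactate is too high, "the study drug will be held until the next scheduled dose the following day" (section 6.1.6). That section also lists holds for hypoxemia, low hemoglobin and other conditions, and says COHb is not measured on days held for another reason.
- Section 6.1.8 ends dosing permanently after listed events, one of which is a COHb reading of 10% or more. Section 6.1.9 adds death.

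Two statements bear on who is to be analyzed. Section 5.4 commits to using all data from patients extubated before finishing treatment, on a modified intention-to-treat (MITT) basis. Section 9.3 puts everyone with at least one dose into the safety analyses.

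**The concern.** Classical repeated measures ANOVA works on a complete subject-by-day table, so a subject missing one of three days contributes nothing. Here the reasons for a missing day are clinical: recovery (extubation), deterioration (hypoxemia, lactate, death) or COHb itself. The last matters most. A subject whose COHb reaches 10% on Day 1 has no further dosing, hence no Day 2 or Day 3 value, and listwise deletion then also removes the high Day 1 value. The fitted day means would describe patients who were still ventilated on Day 3 and never met a hold.

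At stake are the precision and possible bias of the day-by-day COHb comparison and the lung-physiology results, and consistency with sections 5.4 and 9.3. The lung-physiology models are more exposed. LIS, PaO2/FiO2 and OI span six days (1 to 5, and 7), blood gases after Day 3 are recorded only when available, and OI needs a ventilator pressure.

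**Working it through.** **1. The plan's own sizing figure.** Section 9.2 sizes the trial ("sample size of 36 (2:1 CO:placebo") to estimate the CO-arm mean difference between measured and predicted COHb "within 0.5% with 95% confidence". It continues: "Using a more conservative estimate of standard deviation (SD)=0.6", allows 8% dropout and claims a probability above 99%. The half-width is t(0.975, n−1) × 0.6/√n.

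- n = 24: 2.069 × 0.6/√24 = 0.253.
- n = 22, after 8% dropout: 2.080 × 0.6/√22 = 0.266.
- From the chi-square distribution of the sample variance, the probability of a half-width of 0.5 or less exceeds 0.9999 at both sizes. It is 0.996 at n = 15 and 0.988 at n = 14.

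The claim reproduces and survives the loss of 9 of 24 CO subjects. It does not rest on the ANOVA.

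**2. How likely is any incompleteness?** The only loss rate in the documents is the 8% dropout. Read as the share of subjects with a missing day, it leaves 36 × 0.92 = 33 subjects, and the chance of at least one incomplete subject is 1 − 0.92^36 = 95%. With 10% exit on each of Days 2 and 3, it is 1 − 0.81^36 = 99.95%.

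**3. Complete subjects and loss of precision.** The loss rates and the within-subject correlation (ICC 0.4) are assumptions. Take unit total variance. The mean of k days from one subject has variance v(k) = ICC + (1 − ICC)/k, so v(3) = 0.6, v(2) = 0.7 and v(1) = 1. A mixed model's information per subject on the common mean is the sum of p(k)/v(k), where p(k) is the share of subjects with k days. The classical fit keeps only p(3)/v(3). The ratio of standard errors is the square root of the ratio of information.

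| Pattern | Loss q | p(3), p(2), p(1) | Information: all days vs complete | SE ratio | Complete CO subjects of 24 |
|---|---|---|---|---|---|
| Independent misses, p(3) = (1−q)³ | 10% | 0.729, 0.243, 0.027 | 1.589 vs 1.215 | 1.14 | 17.5 |
| Independent misses | 20% | 0.512, 0.384, 0.096 | 1.498 vs 0.853 | 1.32 | 12.3 |
| Exit after Day 1, no return, p(3) = (1−q)² | 10% | 0.81, 0.09, 0.10 | 1.579 vs 1.350 | 1.08 | 19.4 |
| Exit after Day 1, no return | 20% | 0.64, 0.16, 0.20 | 1.495 vs 1.067 | 1.18 | 15.4 |

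The two patterns miss similar shares of days. Exit without return misses (0.10 + 0.19)/3 = 9.7% or (0.20 + 0.36)/3 = 18.7%. Holds can behave like the first pattern; extubation, death and permanent discontinuation follow the second. In the placebo arm, 20% exit leaves 12 × 0.64 = 7.7 complete subjects for a model with three entry groups and a three-way interaction. For six-day endpoints, 10% independent misses leave 0.9^6 = 53% complete.

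**4. Direction of bias.** As a limiting case, suppose Day 1 COHb is normal and the highest 10% of subjects exit. The complete-case Day 1 mean falls by φ(1.282)/0.90 = 0.1755/0.90 = 0.195 SD. The Day 3 mean falls by 0.4 × 0.195 = 0.08 SD. For the highest 20%, the falls are 0.280/0.80 = 0.35 SD and 0.4 × 0.35 = 0.14 SD.

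A small simulation (150 runs per setting, ICC 0.5, exit depending on the previous day's COHb at an assumed strength) gave the same sign. Complete-case bias in the Day 3 CO mean was −0.07, −0.12 and −0.14 COHb points at 10%, 20% and 30% loss. Mixed-model bias was between −0.008 and +0.010. Without selection both were essentially unbiased. The sizes depend on the assumed strength of selection; the sign is what carries over.

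**The case against.** A reader might infer that the plan prescribes listwise deletion. It does not. No complete-case rule or software is stated, and sections 5.4 and 9.3 point toward using all data. What stands against the plan is that the named method, in its ordinary form, would not deliver that commitment, and nothing rules that form out.

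A reader might also infer that the accuracy co-primary endpoint would rest on a depleted sample. The documents do not support this. Section 9.4.2 says "The mean difference between predicted and measured COHb levels with 95% confidence intervals will be presented for the iCO group", and adds daily summaries, Spearman correlation, Bland-Altman plots and regression. None needs three complete days. The high readings are also still counted in the separate comparison of COHb of 10% or more. The COHb contrast between arms should be large by design, so a standard error 1.1 to 1.3 times larger is unlikely to reverse that conclusion.

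Nor do the documents support calling missing days certain or the loss large: 8% dropout is the only rate given. Doses stopped early are not missing, because section 8.5.3 takes the 90-minute measurements at the stop.

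It is tempting to add that the arms have unequal variances because placebo COHb hardly varies. The Phase I figures in section 2.2.5 do not show this: placebo 1.97 ± 0.39%, 200 ppm 4.9 ± 0.28%, 100 ppm 3.48 ± 0.7%, with four subjects per group. The spread has no consistent direction.

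Finally, a mixed model does not define a 90-minute COHb on an undosed day, or OI after extubation or death. That is correct, and the fix has to cover it. The missing-data methods in section 9.4.3 do not, because they are set out for long-term outcomes.

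**Conclusion.** The point holds as a choice of method that should be changed. Sections 9.4.2, 9.4.3 and 9.4.5 name a method whose classical fit drops every subject with any missing day, while the protocol makes such days very likely and related to patient status. If fitted that way, the day-by-day COHb and lung-physiology results would lose precision, could be biased, and would conflict with sections 5.4 and 9.3.

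At an assumed 10% to 20% loss per day and ICC 0.4, 51% to 73% of subjects are complete under independent misses (SE ratio 1.14 to 1.32), or 64% to 81% under exit without return (1.08 to 1.18). These are illustrations; the documents give no missed-day rate. The bias figures also rest on assumed selection, and the mixed model's advantage on bias assumes that missingness depends on values already observed. The sample size and the main accuracy analyses are not affected.

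**What to change.** In 9.4.2, 9.4.3 and 9.4.5, replace the named method with a linear mixed model for repeated measures, fitted by REML to all observed days from every dosed subject. State the within-subject covariance and a small-sample degrees-of-freedom method, for example Kenward-Roger. Other covariance choices are defensible; what matters is that one is fixed in advance. Arm-specific residual variance for COHb is optional and should not be justified by the Phase I placebo SD.

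Add three statements:

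- Undosed days contribute no 90-minute COHb.
- How days after extubation and after death are treated for LIS, PaO2/FiO2, OI and Vd/Vt.
- A table by arm of days observed and reasons for missing days.

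The change is to the analysis text only. It needs no additional patients, visits or measurements. The one item that takes thought is the rule for post-extubation and post-death days, which the plan needs under any model.

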In our recently completed Phase I fixed dose iCO trial, we also found an excellent correlation between measured and predicted COHb levels using the CFK equation¹¹². While the CFK equation is a well-validated model of CO uptake that accurately predicts the rise in COHb following CO exposure in humans with normal lung function⁹⁷⁻¹⁰³, it had not been previously used in ARDS patients with impaired gas exchange before. We found an excellent correlation in participants treated with 100 ppm iCO (Spearman $r= 0.8614$; $p<0.0001$), but an even stronger correlation in subjects treated with 200 ppm iCO (Spearman $r=0.916$; $p<0.0001$) (Figure 8A). Modeling the 200 ppm Cohort 2 data with linear regression revealed a slope of 1.112 (95% confidence interval [CI] [1.003, 1.22]), a y-intercept of -0.6632 (95% CI [-1.174, -0.1522]), and goodness-of-fit $R^2=0.9204$ ($p<0.0001$). Bland-Altman plots also demonstrated excellent agreement between measured and CFK equation-predicted COHb levels (Figure 8B) with a mean difference between measured and predicted COHb levels of 0.1467 ± 0.2738 in Cohort 2 (200 ppm).

The above predictions using the CFK equation were made using a MATLAB-generated computer program to estimate DLCO using the baseline and 20 minute COHb. The estimated DLCO was then input into the programmed CFK equation and used to predict the 60, 75, and 90 minute COHb levels. This program was validated by generating the previous published curves (Figure 1) that were derived from predicted values using the CFK equation¹⁰¹.

[figure not shown]

Figure 8. CFK equation accurately predicts COHb levels in ARDS patients.

CFK Equation For Precision-Based iCO Dosing

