6.1.3 DOSING AND ADMINISTRATION

Inhaled CO or placebo air will be administered to participants via the COventDS, which will be calibrated and connected to the ventilator (**Figure 9**). Ventilator management will follow the ARDS Network lower tidal volume (6 mL/kg PBW) protocol¹³. Subjects randomized to CO will be administered iCO at 200 ppm for 20 min as a “test dose” on each treatment day to determine in real-time each subject’s CFK equation-determined personalized dose.

COHb levels will be measured before and after the 20 min test dose, and these two levels entered into the CFK equation calculator program to estimate DL_{CO} and compute the iCO dose to achieve a COHb level of 7% (target 6-8%) at 90 min. After the iCO dose is determined, subjects will be administered iCO at the CFK equation-determined personalized dose (200-500 ppm) but **not to exceed 500 ppm or 90 min total (including test dose)**. Subjects randomized to placebo will be administered medical grade air.

The study drug will be administered for up to 90 minutes daily for three days following randomization or until discontinuation of mechanical ventilation, whichever occurs first. For patients who have a tracheostomy, the equivalent of extubation for the purposes of this protocol will be breathing via tracheostomy with unassisted breathing.

The study drug concentration will be monitored continuously with the COventDS built-in analyzer and blood will be drawn at serial time points for arterial blood gas (ABG) analysis and safety monitoring of COHb levels as described in **Section 6.1.4**.

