6.1.5 CO DOSING ALGORITHM USING THE CFK EQUATION

For subjects randomized to iCO, iCO (200 ppm) will be administered for up to 20 minutes as a "test dose" on each day to determine the subject's CFK equation-determined dose. The COHb level will be measured prior to the test dose and 20 minutes after the test dose. These two COHb levels will be used in the CFK equation to determine each subject's specified dose in order to achieve a COHb level of 6-8%. After the CO dose is determined, subjects will be administered inhaled CO at the algorithm-determined dose- not to exceed 500 ppm or 90 minutes total (including test dose). Subjects randomized to placebo will be administered medical grade air.

1. Arterial or venous blood will be drawn for baseline blood gas analysis and COHb measurements prior to iCO or placebo administration.
2. Subjects randomized to CO will be treated with inhaled CO at 200 ppm for 20 minutes (test dose).
3. After 20 minutes, blood will be drawn for COHb measurement.
4. DLCO will be estimated using the baseline and 20 min COHb in the CFK equation calculator program, and used to compute the iCO dose to achieve a COHb level of 7% (target 6-8%) at 90 minutes.
5. Dose will be adjusted (200-500 ppm) in subjects randomized to CO based on CFK equation-determined dose.
6. Blood will be drawn for COHb measurements at 20 min, 40 min, 60 min, 75 min, 90 min, and 3 hours. Blood will also be drawn for blood gas analysis at 90 min.

On days 1-3, a total of approximately 3 mL of blood will be drawn during the study drug administration for safety monitoring of COHb levels and blood gas analysis.

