8.5.3 STUDY DRUG ADMINISTRATION AND MONITORING

The study drug will be administered for up to 90 minutes daily for up to 3 days following randomization or until discontinuation of mechanical ventilation, whichever occurs first according to **Section 6.1.9**. See **Sections 6.1.6, 6.1.7, and 6.1.8** for information about study drug hold, interruption, and permanent discontinuation criteria.

Study Drug Dosing:

Subjects randomized to CO will be administered iCO at 200 ppm for 20 min as a “test dose” on each treatment day to determine in real-time each subject’s CFK equation-determined personalized dose. COHb levels will be measured before and after the 20 min test dose, and these two levels entered into the CFK equation calculator program to estimate DL_{CO} and compute the iCO dose to achieve a COHb level of 7% (target 6-8%) at 90 min. After the iCO dose is determined, subjects will be administered iCO at the CFK equation-determined personalized dose (200-500 ppm) but not to exceed 500 ppm or 90 min total (including test dose). Subjects randomized to placebo will be administered air.

Monitoring during Study Drug Administration:

Subjects will be monitored with continuous pulse oximetry, cardiac monitoring, and either intermittent (at least every 15 minutes) or continuous blood pressure monitoring (if an arterial line is in place) throughout the course of the 90-minute study drug treatment.

$SpCO$ and SpO_2 will be monitored continuously using a Masimo Rad-7 non-invasive pulse oximeter, and recorded at the time points specified in **Table 5**. COHb levels will be measured using an IL GEM Premier Co-oximeter and recorded at the time points specified below. Arterial or venous blood will be drawn for blood gas analysis prior to treatment and at the completion of study drug administration (90 min or earlier if discontinued prior to 90 min). If study drug treatment is discontinued prior to 90 min, all of the scheduled 90-minute measurements will be made and recorded at the time of study drug discontinuation. Ambient CO levels will be monitored continuously using a Dräger Pac 7000 CO detector, and recorded at the time points specified below.

Table 5. CO Monitoring During Treatment

| | ABG or VBG (pH, PCO_2 , PO_2) | FiO_2 | COHb level (IL GEM Premier co-oximeter) | CO Dose Adjustment (CFK calculator) | $SpCO$ (Masimo Rad-7) | SpO_2 (Masimo Rad-7) | Ambient CO Level (Dräger Pac CO detector) |

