9.4.5 SAFETY ANALYSES

The primary endpoint is safety of iCO, defined by the incidence of pre-specified administration-related AEs and SAEs. Administration-related SAEs are: 1) myocardial infarction; 2) stroke; 3) new onset arrhythmia requiring DC cardioversion; 4) worsening hypoxemia^{1,2}; 5) COHb \geq 10%; and 6) increase in lactate by \geq 2 mmol/L. The primary endpoint is also accuracy of the CFK equation-based personalized iCO dosing algorithm to achieve a COHb level of 6-8%.

We will examine all AEs including pre-specified administration-related AEs by the type of event, as well as by body system class, and will report proportions and 95% CI. We will compare the occurrence of specific AEs in each arm by the χ^2 test, and the number of AEs per patient in each arm by the Wilcoxon-Mann-Whitney test.

For AEs not included in the protocol defined grading system, the CTCAE Version 5.0 guidelines will be used to describe severity. The CTCAE term, start and stop date, severity, relationship, expectedness, and outcome will be reported for all AEs. A separate table will report the incidence of pre-specified administration-related AEs per arm.

COHb levels will be summarized descriptively reporting mean, standard deviation, median, minimum, and maximum at each time point, each day, by treatment arm. The mean difference between predicted and measured COHb levels with 95% confidence intervals will be presented for the iCO group. Repeated measures analysis of variance (ANOVA) will be used to assess the effects of treatment, time (over 3 days), and the interaction between time and treatment for 90-minute COHb levels. ANOVA will be repeated to assess the effects of treatment, time (over 3 days), entry criteria (ARDS/Sepsis vs. Non-ARDS/Sepsis Pneumonia vs. Non-ARDS/non-Sepsis Pneumonia), and two-way/three-way interactions of time, treatment and entry criteria. We will also compare the occurrence of COHb $\geq 10\%$ in each arm by the χ^2 test.

Accuracy of the CFK equation-based personalized iCO dosing algorithm to achieve target COHb levels will also be analyzed by Spearman correlation and Bland-Altman plots using measured vs. predicted COHb levels and modeled using linear or non-linear regression.

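### Dosing to a predicted 7% makes the 90-minute prediction constant, so the planned Spearman correlation and measured-on-predicted regression say nothing about dosing accuracy at the endpoint time

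*Combined protocol and SAP*

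**What the plan says.** The dosing rule is explicit. After a 20-minute test dose the calculator estimates DLCO and is used, in section 6.1.3, to "compute the iCO dose to achieve a COHb level of 7% (target 6-8%) at 90 min"; sections 6.1.5, 8.5 and 8.5.3 repeat the rule. The dose is confined to 200-500 ppm.

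Section 3 defines accuracy, the second primary endpoint, as measured 90-minute COHb set against 6-8%. For its analysis, section 9.4.2 says: "Accuracy of the CFK equation-based personalized iCO dosing algorithm to achieve target COHb levels will also be analyzed by Spearman correlation and Bland-Altman plots". Section 9.4.5 repeats this and completes it: "using measured vs. predicted COHb levels and modeled using linear or non-linear regression". Neither section defines the prediction or names its time point.

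Section 9.4.2 also plans descriptive COHb summaries by time point, day and arm, and this: "The mean difference between predicted and measured COHb levels with 95% confidence intervals will be presented for the iCO group". No proportion of sessions within 6-8% is planned in section 9.4.

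In the fixed-dose Phase I trial, section 2.2.9 reports a Spearman coefficient of 0.8614 at 100 ppm and "an even stronger correlation in subjects treated with 200 ppm iCO", 0.916. Section 9.2 cites the latter as evidence that the equation predicts well.

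**The concern.** In Phase I the dose was fixed and the predicted COHb differed between patients, so a correlation had something to work on. Here the dose is adjusted until the prediction equals the target, which removes the spread of the predictor at the time that defines the endpoint.

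A coefficient can then be obtained only by adding sessions at a dose limit, sessions stopped early, or other time points. Because the plan leaves the prediction and its time point open, that choice falls to the analyst. The risk is that a high pooled coefficient is set beside 0.86-0.92 and read as confirming the dosing algorithm, when it mainly shows that COHb rises during exposure.

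**Working it through.** **1. The plan's own accuracy figure.** Section 9.2 uses SD 0.6, 24 iCO subjects and 8% dropout (about 22 left), with precision of 0.5. Expected 95% CI half-width at n = 22: 2.08 × 0.6/√22 = 0.27. The probability that the half-width is at most 0.5 exceeds 0.9999, and 0.1467 ± 0.5 gives -0.353 to 0.647. The stated >99% reproduces. It rests on the mean difference, not on a correlation.

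**2. Full-length session inside the dose limits, 90 minutes.** Let M be measured COHb and P = 7 the prediction.
- Regression slope = cov(M, P)/var(P) = 0/0. Spearman likewise needs variation in the ranks of P. Both are undefined, whatever the spread of DLCO.
- Bland-Altman: d = M − 7 and a = (M + 7)/2, so d = 2(a − 7). Every point lies on a line of slope 2.
- The mean and SD of d are those of M − 7, which is the dosing error itself.

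**3. Adding dose-limited sessions at 90 minutes.** A linear CFK solution was fitted to the 200-500 ppm rows of Table 4 (root mean square error 0.04) and the dosing rule applied in 3,000 simulated trials of 66 sessions (22 patients × 3 days). Assumptions not in the documents: lognormal DLCO with mean 3.45 and the CVs below, baseline COHb 1.5% (SD 0.4), independent sessions. Error has mean 0.1467 and SD 0.2738 (Phase I) or 0.6 (planning value).

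| DLCO CV | Sessions at a limit | Spearman, SD 0.2738 | Spearman, SD 0.6 |
|---|---|---|---|
| 20% | 5.6% | 0.08 | 0.05 |
| 35% | 19.5% | 0.35 | 0.23 |
| 50% | 30% | 0.56 | 0.43 |

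Within a column the error is the same. The coefficient follows the share of sessions at the limit.

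**4. Pooling time points.** A second simulation has 24 subjects × 3 days, baseline 2.0% (SD 0.4), test-dose rise 0.9 (SD 0.25), a linear rise to a predicted 7%, error growing to its full SD at 90 minutes with half its variance between subjects, and measurement SD 0.15. All of these are assumptions.

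| Error SD | Outside 6-8% at 90 min | Spearman, 40-90 min pooled | Minutes on gas in place of prediction | Spearman, 60-90 min pooled |
|---|---|---|---|---|
| 0.6 | 10% | 0.93 | 0.92 | 0.84 |
| 1.0 | 32% | 0.85 | 0.84 | 0.68 |
| 1.5 | 51% | 0.74 | 0.73 | 0.53 |

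Over 40-90 minutes the CFK prediction adds about 0.01 to what the clock alone gives. The CFK-based model of step 3 gives a similar pooled 40-90 minute value at SD 0.6 (0.88-0.90).

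**5. What the valid summaries would show.** Limits of agreement for M − 7, as 0.1467 ± 1.96 × SD:
- SD 0.2738: -0.39 to 0.68, that is COHb 6.61-7.68%, with 99.9% of sessions in range.
- SD 0.6: -1.03 to 1.32, that is COHb 5.97-8.32%. In range: Φ((1 − 0.1467)/0.6) − Φ((−1 − 0.1467)/0.6) = 89.5%.

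With dose-limited sessions included, the in-range share is 90-99.8% (SD 0.2738) or 81-89% (SD 0.6) as the DLCO CV goes from 50% down to 20%.

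**6. Sessions stopped early.** Section 6.1.7 stops treatment above 8% COHb, and section 8.5.3 then takes the scheduled 90-minute sample at stopping. For a dose inside the limits, the model prediction at that earlier moment is below 7%. The plan does not say which prediction applies.

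**The case against.** The wording of 9.4.2 presents these methods as additional. The same section plans the mean difference with a 95% CI and descriptive SDs, and the sample size rests on that mean difference. This stands: the accuracy endpoint does not depend on the correlation.

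A reader might infer that the Bland-Altman analysis fails as well. It does not. Against a constant 7%, its bias and limits of agreement are the dosing error; only the trend in the plot is meaningless.

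A reader might also infer that the coefficient cannot tell a good algorithm from a poor one. That goes too far. Pooled over 60-90 minutes, its simulated 5th-95th percentile ranges do not overlap: 0.92-0.95, 0.80-0.88, 0.61-0.75 and 0.45-0.61 at error SDs of 0.2738, 0.6, 1.0 and 1.5. The two largest SDs are 3.7 and 5.5 times the Phase I value, and over 60-90 minutes they would score well below Phase I. The difficulty is calibration. At SD 1.0 the coefficient is 0.68 or 0.85 according to whether the 40-minute reading is included, and the plan does not say which times are used.

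Finally, predictions do vary between patients at 40, 60 and 75 minutes (SD 0.26-0.42 at 40 and 0.17-0.48 at 60 minutes in the model of step 3). Correlation or regression within one of those times can therefore check the CFK model. This stands, but it is a different question from whether dosing reached the target.

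**Conclusion.** The point holds in a limited form. In full-length sessions not held at a dose limit, the 90-minute prediction is 7% by construction, so the planned Spearman correlation and measured-on-predicted regression carry no information on dosing accuracy at the endpoint time. This follows from the dosing rule and needs no simulation. Once dose-limited sessions or several times are pooled, the coefficient mainly reflects the share at a limit or elapsed time, and 0.86-0.92 from Phase I is not a benchmark. The sizes shown depend on the assumed DLCO spread, uptake curve and error SD.

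The documents do not support a claim that the accuracy endpoint cannot be assessed, because valid summaries are already planned. A mean difference alone does not show scatter, however: at SD 0.6 its CI half-width is about 0.27 while about one session in ten inside the dose limits falls outside 6-8%. The text should be corrected before analysis.

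**What to change.** In sections 9.4.2 and 9.4.5:
- Stop using Spearman and measured-on-predicted regression as evidence of dosing accuracy. If wanted, keep them as a check of the CFK model within single times (40, 60 or 75 minutes).
- For accuracy, report 90-minute measured COHb minus 7%: bias, SD and limits of agreement, allowing for repeated days per patient. Add the proportion of sessions within 6-8% with a confidence interval, which matches the section 3 definition.
- Report prediction error for the dose actually delivered, separately by time point. Plot it against delivered dose or estimated DLCO, not against the mean of measured and predicted.
- Define the prediction used for sessions at a dose limit and for sessions stopped early, and flag both.

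The cost is SAP wording and plots; Table 5 already schedules the COHb samples. The downside is the loss of a like-for-like correlation with Phase I.
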